#### **5.2.8.4. Categorization of ECG parameters**

The categorization of QTc will be per ICH E14 guidance:

The absolute QTc interval (QTcF and QTcS) value for each patient will be categorized as  $\leq 450$ ;  $> 450 - \leq 480$ ,  $> 480 - \leq 500$ ;  $> 500$  msec, using the maximum value post baseline (considering both cycles) based on the averaged triplicate values. Similarly, the absolute values of HR, PR and QRS will be categorized as follows: HR  $\leq 50$  bpm, HR  $\geq 120$  bpm, PR  $\geq 220$  msec and QRS  $\geq 120$  msec.

The maximum increase from baseline QTc will be categorized as:  $\leq 30$  msec,  $> 30 - \leq 60$  msec and  $> 60$  msec based on the averaged triplicate values. Similarly, the maximum increase from baseline for HR will be categorized as  $\geq 20$  bpm and maximum increase from baseline for PR will be categorized as  $\geq 20$  msec.

CCI

#### 5.2.10. Analyses for Binary Data

Binary variables will be summarized by frequency counts and percentages. Unless otherwise specified, the calculation of proportions will include the missing category. Therefore counts of missing observations will be included in the denominator and presented as a separate category.

If the analysis refers only to certain cycle or timepoints, then percentages will be based on the number of patients with an assessment at that cycle or timepoint, unless otherwise specified.

Best response will be summarized as a binary variable using frequency counts, percentages, and will additionally include a 95% Clopper-Pearson CI for the rate.

#### 5.2.11. Analyses for Continuous Data

Most continuous variables will be summarized using descriptive statistics i.e., number of non-missing values and number of missing values [i.e., n (missing)], mean, median, standard deviation (SD), minimum, maximum and first and third quartile (Q1 and Q3). Some summaries will also include the coefficient of variation (cv). The values for some continuous variables will be categorized, and will be analyzed as described in Section 5.2.12.

If the analysis refers only to certain cycle or timepoints, then percentages will be based on the number of patients with an assessment at that cycle or timepoints, unless otherwise specified.

For the change from baseline in ECG parameters, including the primary endpoint (the change from baseline in corrected QT interval) will be summarized with descriptive statistics, as above. Additionally, a linear model with the Cycle 1 nominal timepoints as a fixed effect and unstructured variance/covariance to account for the repeated measurements from patients will be used for the primary analysis to estimate the mean change in QTc at the post baseline Cycle 1 nominal timepoints (using least squares mean) along with 2-sided 90% confidence interval for the least squares mean. Confidence intervals will use the approximate t distribution with degrees of freedom by Kenward Rogers method.

ECG parameter results (absolutes) will be summarized with descriptive statistics and a 90% CI for the mean will be calculated using the t-distribution and the observed standard deviation from the particular timepoint.

#### **5.2.12. Analyses for Categorical Data**

Qualitative variables (including some continuous variables where categories are defined) will be summarized by frequency counts and percentages. Unless otherwise specified, the calculation of proportions will include the missing category. Therefore counts of missing observations will be included in the denominator and presented as a separate category.

If the analysis refers only to certain cycle or timepoints, then percentages will be based on the number of patients with an assessment at that cycle or timepoint, unless otherwise specified.

#### **5.2.13. Analyses for Time to Event Data**

Time to event endpoints will be summarized using the Kaplan-Meier method and estimated survival curves will be displayed graphically. Graphs will describe the number of patients at risk over time. The quartiles and probabilities of an event at particular points in time will be estimated by the Kaplan-Meier method. Confidence intervals for quartiles will be based on the Brookmeyer-Crowley method. Confidence intervals for the estimated probability of event at a particular timepoint will be generated using the log(-log) method with back transformation to a confidence interval on the untransformed scale. Summaries of the number and percentages of patients with an event will also be provided on summary tables.

#### **5.2.14. Impact of COVID-19 Pandemic**

The study enrollment was ongoing during the COVID-19 pandemic period. Data summaries and analyses will be performed to assess the impact of COVID-19 on the trial population and study data.

An anchor date will be used as a start date for COVID-19 pandemic related periods **CCI**

For global pandemic reference date: the date World Health Organization designated COVID-19 as a global pandemic - March 11, 2020.

For China reference date: the date COVID-19 was identified as the causative agent of outbreak in Wuhan by the China Center for Disease Control and Prevention - January 9, 2020. (This study has no sites in China).

When producing data summaries intended to show the potential impacts of COVID-19 on the study, data will be presented as “before” and “during,” where the anchor date is included in the “during” group.

A different anchor date may be used for purposes of regulatory submission if requested by a regulatory authority.

### **5.3. Methods to Manage Missing Data**

#### **5.3.1. Missing Dates**

In data listings, dates will reflect the information provided by the investigator on the CRF, if any imputation was applied to data presented in listings, such data will be clearly marked as imputed.

##### **5.3.1.1. Missing or Partial Adverse Event dates/times**

Complete adverse event dates are needed to determine treatment emergence, and to assign adverse events to cycles, therefore missing or partial dates will be imputed. Completely missing AE dates will be imputed as follows with the end result that the events will be considered treatment emergent.

**AE Start Date:** If the AE start date is missing, and if the date of first dose is less than AE end date, then the start date will be assigned as the date of first dose. Otherwise if the date of first dose is after the AE end date then the AE start date will be imputed as the earliest of non-missing AE end date or informed consent date.

**AE Stop Date:** If the AE end date is missing then the end date will be imputed as the latest of the Subject Withdrawal/Completion date, death date, last dose of study treatment, or AE start date.

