### **5.2.5. Assignment to Cycles**

Data collected in log pages, such as adverse events, and laboratory results, will be assigned to cycles. Cycles are defined in Section 5.2.4. For adverse events, the assignment will be based on the start date. Adverse events that start after the end of the last cycle will be assigned to a cycle called Follow-up.

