#### **5.3.1.5. Other Missing or Partial Dates**

Imputation methods for other missing or partial dates which will be used in computations of durations will be as follows (e.g. date of diagnoses):

- If the day of the month is missing for a start date used in a calculation, the first day of the month will be used to replace the missing date.

- If both the day and month are missing, the first day of the year is used.
- For stop dates, the last day of the month, or last day of the year is used if the day or day and month are missing, respectively.
- If the date is completely missing, no imputation will be performed (other than as explicitly described in this section).

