#### 6.6.1.1. VOD

Summaries focused on VOD/SOS (The MedDRA PTs of Venoocclusive liver disease and Venoocclusive disease) will include the following number and percentage of patients out of the following groups (denominator):

- Any VOD with denominator of safety analysis set
- VOD before (first) follow-up HSCT with denominator of safety analysis set
- VOD before (first) follow-up HSCT with denominator of safety analysis set with a prior HSCT
- VOD after follow-up HSCT with denominator of safety analysis set with a follow-up HSCT
- VOD after follow-up HSCT with denominator of safety analysis set with both a prior and a follow-up HSCT.

Timing relative to study treatment and HSCT (days): The timing of the first VOD relative to the nearest prior GO dose will be summarized with descriptive statistics (VOD start date – nearest GO dose date +1). The timing of the first HSCT relative to the nearest VOD after the

HSCT date (days) will be summarized with descriptive statistics (VOD start date – first HSCT date +1).

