**HEAMORRHAGE:**

SMQ:

Haemorrhage terms (excluding laboratory terms) (SMQ narrow)

**MYELOSUPPRESSION:** AEs encoded to MedDRA preferred terms (PTs) within the following SMQ:

- Haematopoietic thrombocytopenia (SMQ narrow and broad)
- Haematopoietic leukopenia (SMQ narrow)
- Haematopoietic erythropenia (SMQ narrow and broad)
- Haematopoietic cytopenias affecting more than one type of blood cell (SMQ narrow)

**INFECTIONS: Grade  $\geq 3$  AEs and/or serious** AEs encoded to MedDRA preferred terms (PTs) within the following SOC and HLT

SOC (General infections):

- Infections and Infestations SOC

HLTs (Lung infections):

- Bacterial lower respiratory tract infections
- Fungal lower respiratory tract infections
- Lower respiratory tract infections NEC

- Respiratory tract infections NEC
- Viral lower respiratory tract infections

**INFUSION RELATED REACTIONS (including Anaphylaxis):** From start of infusion to within 24 hours of end of infusion:

Include events that occurred from start of infusion to within 24 hours of end of infusion:

SMQ:

- Anaphylactic reaction (SMQ narrow)
- Angioedema (SMQ narrow)
- Hypersensitivity (SMQ narrow)

PT:

- Cytokine release syndrome
- Infusion related reaction
- Chills
- Pyrexia
- Hot flush
- Flushing
- Feeling hot
- Hyperhidrosis
- Dizziness
- Dyspnoea
- Wheezing
- Tachycardia
- Hypotension

Thus only AEs that start within a window according to the treatment exposure records of the start of the GO infusion in terms of date and time to 24 hours after the date and time of the stop of the infusion. Since the AE CRF collects only AE start date and not start time, the AE start date will be compared to the date part only of the exposure window (rather than using imputed time of AE start).

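### The first-dose date given to an undated adverse event also decides VOD/SOS order and timing around transplant, and an undated event that ended on the first-dose date gets no start date

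*SAP*

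**What the plan says.** SAP 5.3.1.1 says complete AE dates are needed for two purposes, judging treatment emergence and assigning events to cycles, and "therefore missing or partial dates will be imputed". The algorithm is then introduced with "Completely missing AE dates will be imputed as follows with the end result that the events will be considered treatment emergent". Its parts are:

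- Start date missing: "if the date of first dose is less than AE end date, then the start date will be assigned as the date of first dose". If the first dose falls after the AE end date, the start is instead the earlier of the end date and the consent date.
- End date missing: the latest of withdrawal/completion, death, last dose or AE start.

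The AE start date is used in several other places:

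- SAP 5.2.5, cycles: "For adverse events, the assignment will be based on the start date".
- SAP Appendix 2, infusion-related reactions: "the AE start date will be compared to the date part only of the exposure window".
- SAP 6.6.1.1, VOD/SOS: rows before and after transplant, including "VOD before (first) follow-up HSCT with denominator of safety analysis set", plus days from the nearest prior GO dose and from the first HSCT.

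SAP 5.3.1 has imputed dates marked in listings and says nothing comparable for tables. SAP 5.3.1.5, on other dates used to compute durations, says "If the day of the month is missing for a start date used in a calculation, the first day of the month will be used".

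**The concern.** The rule is built to make an undated event treatment-emergent, and it does that. The same imputed date is then available to every output that reads the AE start date, and for those outputs Cycle 1 Day 1 is not a neutral value. It is the earliest possible on-treatment date, it lies inside the infusion-reaction window, and it precedes any follow-up transplant.

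VOD/SOS matters most. Its risk with previous or subsequent HSCT is one of the post-marketing requirements listed in the Protocol Summary, and it is collected for 12 months, so a true onset can be months after dosing. The case count is likely to be low, so one re-dated case can change the before/after split.

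Two drafting gaps sit beside this. An AE ending on the first-dose date satisfies neither branch. Partial start dates are promised imputation without a method, which leaves the choice to the programmer.

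**Working it through.** The plan gives no figure to reproduce here. The check applies the written rules to invented dates.

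**1. The start-date rule.** Let F be the first-dose date, E the AE end date (or its imputed value) and C the consent date. For a completely missing start:

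- F < E: start = F
- F > E: start = the earlier of E and C
- F = E: no rule

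**2. Examples.** F = 15 Jan 2020, C = 2 Jan 2020.

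| Event, start not recorded | True start | E | Assigned start |
|---|---|---|---|
| Pyrexia | 9 Feb | 12 Feb | 15 Jan |
| VOD, follow-up HSCT on 1 May | 20 May | 10 Jun | 15 Jan |
| Any AE, end also missing (imputed as 1 Dec) | any | 1 Dec | 15 Jan |
| AE that ended on the first-dose date | unknown | 15 Jan | none |
| AE that ended before dosing | unknown | 10 Jan | 2 Jan |

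The pyrexia, a listed infusion-reaction term, becomes a Day 1 infusion reaction in Cycle 1. The third row shows that a missing end date leads back to F in nearly every case.

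**3. The VOD case in SAP 6.6.1.1.**

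- Row: 15 Jan precedes 1 May, so it is counted before follow-up HSCT.
- Days from GO (VOD start − nearest prior dose + 1): 15 Jan − 15 Jan + 1 = 1. With one cycle and the last dose on Day 7 (21 Jan), the true value is 10 + 29 + 31 + 30 + 20 = 120, plus 1 = 121.
- Days from HSCT: truly 20 May − 1 May + 1 = 20. After imputation there is no VOD following the transplant, so the case drops out of this summary.

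**4. Weight of one case.** The documents give no expected number of follow-up transplants. Assuming 5 to 15, one case is 1/5 = 20% to 1/15 = 6.7% of the after-transplant denominator. It adds 1/50 = 2% to the before-transplant row for 50 adults.

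**5. Partial dates, only if SAP 5.3.1.5 were applied to AEs.** Take a start with the day missing and a true onset k days after a reference date (first dose or HSCT), with reference dates spread evenly over three calendar years (1,095 days / 36 months = 30.4 days per month). First-of-month falls before the reference unless the reference is itself the first of the month or the onset is in a later month. The share is about 1 − (k + 1)/30.4.

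| Reference | k (days) | Share placed before it |
|---|---|---|
| First dose | 0 | 97% |
| First dose | 3 | 87% |
| First dose | 6 | 77% |
| First dose | 14 | 51% |
| First dose | 20 | 31% |
| HSCT | 7 | 74% |
| HSCT | 14 | 51% |
| HSCT | 21 | 28% |
| HSCT | 30 | 0% |

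Protocol Table 4 places classical VOD/SOS in the first 21 days after HSCT, the range in which re-ordering would be common.

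**The case against.** The case for leaving the text alone has weight.

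- **Exposure is small.** Every VOD/SOS case is an SAE for 12 months (Protocol 8.1.4.1, 8.4.3), reportable within 24 hours, and the investigator must obtain adequate information (Protocol 8.1). A wholly missing onset date should be rare. This stands and limits the size of the point. It does not make the written rule right when it is used.
- **Listings show the imputation.** True, but a table reader would not see it.
- **The convention errs toward inclusion.** For infusion reactions and cycle tables that is a defensible safety choice, and removing undated events could undercount. This stands, and the fix leaves those tables inclusive.
- **The boundary gap is an edge case with a stated intent.** SAP 3.5.1 treats same-day events as on-treatment. The intent is clear, but the algorithm does not deliver it.

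Some stronger readings are tempting, and the documents do not support them:

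- That the first-dose rule discards a known month. It is introduced for completely missing dates only.
- That first-of-month is the rule for partial AE dates, so early events are lost as pre-treatment. SAP 5.3.1.4 refers concomitant medications to 5.3.1.5, but 5.3.1.1 does not refer AEs there. Death and follow-up therapy dates have their own rules (5.3.1.2, 5.3.1.3). The shares in step 5 are therefore conditional.
- That a VOD dated only to the month of transplant must have followed it. With the last dose on 26 March, HSCT on 10 June and onset recorded as June, onset could be 1 to 9 June. The record supports at least 5 + 30 + 31 + 1 + 1 = 68 days from GO and leaves the order open.
- That infusion reactions are a named post-marketing requirement. The Protocol Summary lists VOD/SOS with HSCT, hemorrhage, QT prolongation and anti-drug antibodies.

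**Conclusion.** The point holds in limited form. Two parts follow directly from the written rule: a completely undated post-transplant VOD/SOS that ended after first dose is tabulated as before follow-up HSCT and 1 day from GO, and an undated AE that ended on the first-dose date receives no start date. The third part is an omission: partial AE start dates have no written rule.

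The first-dose rule does not change overall AE incidence. It changes only cycle, infusion-reaction and before/after-transplant classification, and VOD/SOS timing. The primary QTc analysis is untouched. How often AE dates are incomplete is not stated and is probably low. The 6.7% to 20% weight of one case rests on an assumed 5 to 15 follow-up transplants. This is a minor correction, worth making because it bears on a regulator-requested safety summary and costs little.

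**What to change.** Amend SAP 5.3.1.1, with a cross-reference in 6.6.1.1:

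1. Make the first comparison inclusive (first dose on or before the AE end date), so that an AE ending on the first-dose date starts that day.
2. Do not use imputed start dates for VOD/SOS order or timing relative to HSCT and GO. Query the onset date. If it stays unresolved, show the case as date incomplete unless the known month or the end date settles the order.
3. For partial AE start dates, keep the known month and year, or year alone. Use the first-dose date when these match those of first dose, otherwise the first day of the known period. Never impute a start later than the AE end date. Without that cap, first dose 20 March with an AE recorded as starting in March and ending 10 March would be given a start after its end.
4. Keep the inclusive convention in the infusion-reaction and by-cycle tables, and footnote how many events were placed there by an imputed date.

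The cost is SAP wording, minor programming and a few site queries before database release. The downside is an occasional date-incomplete row in the VOD table.

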##### **5.3.1.2. Missing or Partial Death Dates:**

Missing or partial death dates will be imputed based on the last contact date:

- If the entire date is missing it will be imputed as the day after the date of last contact (see derivation of date of last contact in Section 5.2.6); or
- If the day or month is missing, death will be imputed to the maximum of the full (non-imputed) day after the date of last contact and the following:
  - Missing day: 1st day of the month and year of death, or
  - Missing day and month: January 1st of the year of death.

##### **5.3.1.3. Missing or Partial Anti-cancer Treatment dates**

Incomplete dates for new (follow-up) anti-cancer treatment will be imputed as follows:

- The end date of new anti-cancer therapy will be included in the imputation for start date of new anti-cancer therapy. If the end date of new anti-cancer therapy is:
  - completely missing then it will be ignored in the imputations below,
  - partially missing with only year available then the imputations below will consider 31DECYYYY as the end date of the new anti-cancer therapy, or
  - partially missing with only month and year available then the imputations below will consider the last day of the month for MMMYYYY as the end date of the new anti-cancer therapy.
- If the start date of new anti-cancer therapy is completely or partially missing then the imputed start date of new anti-cancer therapy will be:
  - = 31DECYYYY, if only Year is available and Year < Year of min (last dose of study treatment + 1, end date of new anti-cancer therapy)
  - = Last day of the month, if both Year and Month are available and
    - Year = Year of min (last dose of study treatment + 1, end date of new anti-cancer therapy)
    - Month < Month of min (last dose of study treatment + 1 day, end date of new anti-cancer therapy)
    - = min (last dose of study treatment + 1, end date of new anti-cancer therapy), for all other cases.

#### **5.3.1.4. General concomitant medications and concomitant non-drug procedures**

If start dates of concomitant medications or concomitant non-drug treatments are completely missing, the medications and non-drug treatments/procedures will be considered concomitant unless the medication stop date is prior to first study treatment. If only partial information are available, (e.g. only a month and year or only a year) dates will be imputed (see Section 5.3.1.5) and thus if the imputed dates based on the partial information provides sufficient information to indicate the dates are prior to the start of study treatment (e.g. month/year less than month/year of first dose) then these will be considered to have started prior to treatment; otherwise these will be considered to have started after treatment.

#### **5.3.1.5. Other Missing or Partial Dates**

Imputation methods for other missing or partial dates which will be used in computations of durations will be as follows (e.g. date of diagnoses):

- If the day of the month is missing for a start date used in a calculation, the first day of the month will be used to replace the missing date.

- If both the day and month are missing, the first day of the year is used.
- For stop dates, the last day of the month, or last day of the year is used if the day or day and month are missing, respectively.
- If the date is completely missing, no imputation will be performed (other than as explicitly described in this section).

### **5.3.2. Missing Toxicity Grades of Adverse Events**

In summaries which present maximum toxicity grade, the maximum of non-missing grades will be displayed. A patient will be counted as a missing grade only when all occurrences for a particular event are reported as missing.

### **5.3.3. Missing absolute WBC differential counts and Normal Ranges**

For WBC differential counts (total neutrophil [including bands], lymphocyte counts), the absolute value will be used when the results are reported in this manner. When only percentages are available the absolute value will be derived as follows:

$$\text{Derived differential absolute count} = (\text{WBC count}) \times (\text{Differential \% value} / 100)$$

If both the absolute and % value for Neutrophils or Lymphocytes are reported from the same laboratory sample date and patient, only the absolute value will be graded. The % value will not be graded in this scenario.

If the % value is converted to the differential absolute count for grading and the LLN for the differential absolute count is not available (only LLN for % is available) then Grade 1 will be assigned if the following conditions are met:

- Lymphocyte count decreased:
  - derived absolute count does not meet Grade 2-4 criteria, and
  - % value < % LLN value, and
  - derived absolute count  $\geq 800/\text{mm}^3$
- Neutrophil count decreased
  - derived absolute count does not meet Grade 2-4 criteria, and
  - % value < % LLN value, and
  - derived absolute count  $\geq 1500/\text{mm}^3$

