Appendix 3. Laboratory Tests

Hematology Panel	Chemistry Panel	Coagulation Panel	Urinalysis
WBC/differential counts including blast	Sodium	international normalized ratio/prothrombin time (INR/PT)	pH
RBC count	Potassium	Activated Partial thromboplastin time (aPTT)	Protein/albumin
Hemoglobin	Magnesium		Glucose
Hematocrit	Total calcium		Blood/hemoglobin
Platelet count	Creatinine	Fibrinogen	Ketones/acetone
	Albumin		
	Alanine aminotransferase (ALT)		
	Aspartate aminotransferase (AST)		
	Glucose		
	Total Bilirubin		
	Blood urea nitrogen (BUN)		
	Uric acid or urate		
	Alkaline phosphatase (ALK-P)		
	Lactate dehydrogenase (LDH)		

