### **3.5.2. Laboratory Data**

Laboratory data will be graded programmatically according to the NCI CTCAE v4.03 severity grade (including low and high values if both are defined for the parameter) for the following safety laboratory parameters:

- Hematology tests: hemoglobin, white blood cells, platelets, neutrophils, lymphocytes.
- Chemistry tests: sodium, potassium, magnesium, glucose, creatinine, total calcium, , albumin, total bilirubin, AST, ALT, alkaline phosphatase (ALP). For laboratory tests that can be either abnormally high or abnormally low, both directions will be computed.
- Coagulation tests: prothrombin time, international normalized ratio (INR), activated partial thromboplastin time, fibrinogen.
- Urinalysis test: protein

The non-CTC graded laboratory tests red blood cells, hematocrit, BUN, LDH, uric acid or urate along with urinalysis tests (pH), will be categorized as below normal limit, within normal limits, and above normal limits. The remaining urinalysis tests (albumin, glucose, blood/hemoglobin, ketones/acetone) will be categorized as negative or positive.

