Several laboratory tests have bi-directional grading criteria defined so that both low (hypo) and high (hyper) values will be graded separately. Each criterion will be summarized separately. In the cases where a value is graded as a Grade 1, 2, 3, or 4 for one of the directions, that value will also be assigned as a Grade 0 for the opposite direction for that test. For example, a value meeting the criteria for Grade 3 Hypercalcemia will be classified as a Grade 0 Hypocalcemia.

The following summaries will be provided for the safety analysis set.

The denominator for percentages will be the number of patients treated in the group being summarized with at least 1 post baseline assessment of the laboratory parameter.

Displays will be organized by laboratory category: Hematology parameters including coagulation parameters will be summarized together, chemistry parameters will be summarized together, and urinalysis parameters will be summarized together. Laboratory parameters with CTCAE grades will be summarized separately from laboratory parameters with no CTCAE grades.

For each CTCAE term, patients will be counted according to the worst (maximum) CTCAE grade on treatment (excluding baseline values). Baseline is defined in Section 3.4. If there are multiple assessments that meet the baseline definition on the same day without the ability

to determine which was truly last, then the worst CTC grade will be assigned as the baseline CTC grade.

The following summary tables will be created:

- Shift summary of laboratory parameters of baseline CTCAE grade by maximum post baseline CTCAE grade.
- Shift summary of laboratory parameters from  $\leq$  Grade 2 at baseline to  $\geq$  Grade 3 post-baseline.

The non-CTC graded laboratory tests (red blood cells, hematocrit, BUN, LDH) along with urinalysis test (pH) will be presented according to the following categories overall: below normal limit, within normal limits, and above normal limits. In the unlikely event that for a given participant, clinically significant abnormalities are noted in both directions (eg,  $>$  ULN and  $<$  LLN), then both abnormalities are counted. The remaining urinalysis tests (albumin, glucose, blood/hemoglobin, ketones/acetone) will be categorized as negative or positive.

A shift summary of laboratory test results with no CTCAE criteria of baseline assessment by worst on-treatment assessment will be created. .

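### When only percentages and percentage limits are available, SAP 5.3.3 can grade a normal or high neutrophil or lymphocyte count as Grade 1 decreased, because the rule puts no upper limit on the count

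*SAP*

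**What the plan says.** SAP 3.5.2 sets the general rule: "Laboratory data will be graded programmatically according to the NCI CTCAE v4.03 severity grade". For neutrophils and lymphocytes, SAP 5.3.3 grades the absolute count where it is reported. If both the count and the percentage are reported, "only the absolute value will be graded. The % value will not be graded in this scenario". If only a percentage is reported, the count is derived from the WBC.

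A further fallback applies "If the % value is converted to the differential absolute count for grading and the LLN for the differential absolute count is not available", that is, when only the percentage LLN exists. Grade 1 then needs three conditions together:

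- "derived absolute count does not meet Grade 2-4 criteria, and"
- the percentage "value < % LLN value"
- a derived count of at least 800/mm³ for lymphocytes or at least 1,500/mm³ for neutrophils.

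SAP 6.6.3 repeats the conversion and refers back to 5.3.3 for the detail. It adds no further condition. The grades feed a table described as "Shift summary of laboratory parameters of baseline CTCAE grade by maximum post baseline CTCAE grade".

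Two features of the trial bear on this. Protocol Appendix 3 lists "WBC/differential counts including blast" in the hematology panel. Protocol 4.1 admits patients with WBC below 30,000/µL.

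**The concern.** The first and third conditions both bound the derived count from below. The only condition that could make it low is the one on the percentage, and a percentage below its LLN implies a low count only when the WBC is not raised. In AML, circulating blasts can take up part of the differential and push the neutrophil and lymphocyte percentages down while the counts stay normal or high. The grades concerned describe decreased counts, so such a record would be graded for an abnormality that it does not show.

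At stake is the starting row in the shift table. A patient with a normal count at baseline who is placed in the Grade 1 row, and who later reaches Grade 3 or 4, appears as a worsening of existing cytopenia and not as a fall from normal.

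**Working it through.** The plan gives no figure to reproduce here. The check applies the rule as written and compares it with grading the same derived count against an absolute LLN.

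**Inputs from the documents.** Derived count = WBC × percentage / 100, with floors of 1,500 and 800/mm³ (SAP 5.3.3). Entry WBC is below 30,000/µL (Protocol 4.1).

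**Assumptions.** The documents give no LLN values, so these are assumed:

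| | Percentage LLN (range) | Absolute LLN per mm³ (range) |
|---|---|---|
| Neutrophils | 40% (35–50%) | 1,800 (1,500–2,000) |
| Lymphocytes | 20% (15–25%) | 1,000 (1,000–1,200) |

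**Step 1: the rule as an inequality.** A percentage is below its LLN exactly when the count is below WBC × percentage LLN / 100. The two rules are therefore:

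- Rule as written: Grade 1 if floor ≤ count < WBC × percentage LLN / 100.
- Count-based grade: Grade 1 if floor ≤ count < absolute LLN.

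The written rule uses a limit that rises with WBC. The two limits coincide only at WBC = absolute LLN / (percentage LLN / 100). Above that WBC, false Grade 1 is possible. Below it, false Grade 0 is possible, provided that the absolute LLN exceeds the floor.

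**Step 2: the crossing point.**

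- Neutrophils: 1,800 / 0.40 = 4,500/µL; range 1,500 / 0.50 = 3,000 to 2,000 / 0.35 = 5,714.
- Lymphocytes: 1,000 / 0.20 = 5,000/µL; range 1,000 / 0.25 = 4,000 to 1,200 / 0.15 = 8,000.

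**Step 3: example records under the central assumptions.**

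| WBC/µL | Percentage | Derived count/mm³ | Grade by the rule | Grade against absolute LLN |
|---|---|---|---|---|
| 20,000 | neutrophils 20% | 4,000 | 1 | 0 |
| 20,000 | lymphocytes 10% | 2,000 | 1 | 0 |
| 10,000 | neutrophils 25% | 2,500 | 1 | 0 |
| 5,000 | neutrophils 30% | 1,500 | 1 | 1 |
| 3,000 | neutrophils 30% | 900 | 2–4 | 2–4 |
| 2,000 | neutrophils 80% | 1,600 | 0 | 1 |
| 2,000 | lymphocytes 45% | 900 | 0 | 1 |

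The two rows at WBC 20,000 stay wrong anywhere in the assumed ranges. The neutrophil row at WBC 2,000 is wrong only if the absolute LLN is above 1,600.

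**Step 4: how much of the Grade 1 band is false at WBC 20,000.**

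- Neutrophils: the rule gives Grade 1 from 1,500 / 20,000 = 7.5% up to 40%. It is false from 1,800 / 20,000 = 9% upward. Share: (40 − 9) / (40 − 7.5) = 31 / 32.5 = 95%.
- Lymphocytes: Grade 1 from 4% up to 20%, false from 5% upward. Share: 15 / 16 = 94%.

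These are shares of a percentage band, not of patients.

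**Step 5: the extreme at entry.** As WBC approaches 30,000/µL, Grade 1 extends to neutrophil counts just under 30,000 × 0.40 = 12,000/mm³ (10,500–15,000 over the range). For lymphocytes the figure is 30,000 × 0.20 = 6,000/mm³ (4,500–7,500). This is a corner case.

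**The case against.** The best defence is that the rule seldom operates and that little depends on it. Much of that stands.

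- **Frequency.** The fallback needs an unreported absolute count and a missing absolute LLN. The documents do not say how many records meet both; it could be none. A reader might infer that patients with AML will routinely be graded cytopenic at normal counts. The documents do not support that. Eligibility rests on marrow blasts of at least 5% (Protocol 4.1), screening allows for patients with too few circulating blasts for flow cytometry (Protocol 6.1), and no distribution of WBC or circulating blasts is given. Such records can occur; nothing shows that they are usual.
- **Myelosuppression as an adverse event of special interest (AESI).** A reader might infer that this summary is inflated. It is not: it is built from MedDRA-coded adverse event terms (SAP 3.5.1.1 and Appendix 2) graded by the investigator (SAP 3.5.1), not from programmed laboratory grades.
- **After baseline.** A reader might infer that blast regrowth will appear as a new decrease. The table uses the maximum post-baseline grade, so a false Grade 1 shows only in a patient who never truly reaches Grade 1 or worse for that test. In the Phase 2 study of the fractionated regimen, the 19 responders took a median of 23 days to recover neutrophils to 500/mm³ (Protocol 1.2.2.4), which suggests that masking is common for neutrophils. The protocol gives no such figure for lymphocytes.
- **Direction.** A reader might infer that existing cytopenia is over-counted. The rule also produces false Grade 0 at low WBC, so the net direction is not established.

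None of this supplies the missing upper limit.

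**Conclusion.** The rule is wrong as written, and the consequence is minor. It can assign Grade 1 at a normal or high count and Grade 0 at a low one, because it judges a count by a percentage. The absence of an upper limit follows from the text alone; the WBC levels at which errors begin rest on the assumed LLNs.

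The error moves records only between Grade 0 and Grade 1 for two tests, mainly in the baseline rows of the table of baseline by maximum post-baseline grade. These are not affected:

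- the shift table from Grade 2 or less to Grade 3 or more, since Grades 0 and 1 lie on the same side of its cut;
- recovery times and prolonged cytopenias, which use counts (SAP 3.5.2.1, 3.5.2.2 and 6.6.3.1);
- response (SAP 3.2.3) and the primary QTcF analysis (SAP 6.1.1).

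The correction is worth making because it is cheap, not because a main conclusion depends on it.

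**What to change.** In SAP 5.3.3, replace the percentage-LLN condition; do not add to it. Suggested rule: where the count is derived from a percentage and the record has no absolute LLN, assign Grade 1 if the derived count is at or above the Grade 2 cut-off (1,500/mm³ for neutrophils, 800/mm³ for lymphocytes) and below an absolute LLN. Take that LLN from the same laboratory at another visit or, failing that, from a default range stated in the SAP. If no absolute LLN can be set, report the record as Grade 0/1 not evaluable. That agrees with SAP 6.6.3, which treats a value as gradable only when the ranges needed for grading are present. Grades 2–4 are still taken from the derived count.

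Keeping the percentage condition alongside an absolute limit would remove the false Grade 1 records but leave the false Grade 0 records.

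The cost is one SAP sentence, a small default-range table and a programming change, with no new data. The drawback is that a default range may differ slightly from a site's own.
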